4.3 INCLUSION OF WOMEN AND MINORITIES

Both men and women of all races and ethnic groups are eligible for this trial.

5 SUBJECT REGISTRATION

The Hollings Cancer Center's Sponsor-Investigator Support Unit (SIS Unit) will provide patient registration services for the study. The SIS Unit will conduct a patient eligibility audit review of all eligibility source documents prior to patient registration. These procedures are outlined in the MUSC 103408 Operations Manual. After obtaining signed informed consent and completion of required baseline assessments, eligible subjects will be registered. A unique subject number will be assigned to each patient. The SIS Unit will issue a patient registration confirmation email to the enrolling study team at the time of registration which will include the patient's study ID number.

5.1 SUBJECT RECRUITMENT

Subjects will be recruited from the existing patient population of the Hollings Cancer Center thoracic medical oncology clinics.

5.1.1 INFORMED CONSENT PROCESS

The principles of informed consent are described by Federal Regulatory Guidelines (Federal Register Vol. 46, No. 17, January 27, 1981, part 50) and the Office for Protection from Research Risks Reports: Protection of Human Subjects (Code of Federal Regulations 45 CFR 46). They must be followed to comply with FDA regulations for the conduct and monitoring of clinical investigations.

Informed consent will be obtained by personnel who are qualified by education, training, and experience to perform the task. The Sponsor-Investigator will not use the services of study personnel for whom sanctions have been invoked where there has been scientific misconduct or fraud.

Investigators must ensure that subjects are clearly and fully informed about the purpose, potential risks, and other critical issues regarding clinical studies in which they volunteer to participate. The approved consent form will adhere to the ethical principles that have their origin in the Declaration of Helsinki.

5.1.2 RECRUITMENT METHODS

Subjects will be recruited via internal and external patient referrals to Hollings Cancer Center, multidisciplinary tumor board meetings in which new and ongoing patient cases are reviewed, and the existing patient population of the Principal Investigator and Sub-Investigators.

5.1.3 SETTING

The study will be conducted at Hollings Cancer Center and other potential designated sub-sites to be determined.

6 TREATMENT/STUDY INTERVENTION

6.1 STUDY TREATMENT AND TREATMENT SCHEDULE

This is a traditional safety and efficacy study of Sotorasib and Tarloxotinib for patients with KRAS G12C mutant NSCLC. Treatment will be administered on an outpatient basis.

Sotorasib will be administered at a recommended Phase 2 dose of 960 mg PO daily.

All patients will receive a weekly tarloxotinib infusion at the RP2Dc determined in the safety lead-in portion of the trial administered as a 1-hour IV infusion on Days 1, 8, 15, and 22 of each 28-day cycle until disease progression or unacceptable toxicity. Radiographic tumor assessment including computed tomography (CT) scans or magnetic resonance imaging (MRI) of chest and abdomen will be performed every 8 weeks (\pm 5 days) from Cycle 1 Day 1, using the same imaging modality per patient.

Tarloxotinib dose calculations do not need to be adjusted within a cycle unless the patient has a $>$ 10% change in body weight. Other dose modifications may be required based on QTc prolongation, infusion-related reactions, and other tarloxotinib-related toxicity. In the safety lead-in portion of the study, an initial 3 patients will be treated at Dose Level 1 based on the body weight measured on Day 1 of each cycle (or within 7 days prior [e.g., Day 22 of the prior cycle]). The dose level for subsequent patient cohorts will be determined using standard 3+3 dose escalation/de-escalation rules using the dose levels indicated in table below.

3x3 design to de-escalate tarloxotinib dosing based on DLTs

Dose level	Sotorasib	Tarloxotinib
-2	960 mg PO daily	75 mg/m ² IV weekly
-1	960 mg PO daily	100 mg/m ² IV weekly
0 (full dose)	960 mg PO daily	150 mg/m ² IV weekly

6.2 DEFINITION OF DOSE-LIMITING TOXICITY (DLT)

Toxicities will be graded according to the NCI Common Toxicity Criteria scale version 5.0. If multiple toxicities are seen, the presence of DLT should be based on the most severe toxicity grade experienced. DLT will be defined as any of the following events occurring during treatment with study drugs and is deemed possibly, probably or definitely attributable to the study drugs:

- Any Grade 3 or 4 thrombocytopenia, anemia and/or neutropenia.
- Any other non-hematologic Grade 3 or 4 toxicity that is clinically significant, excluding alopecia.
- Any grade 3 nausea, vomiting or diarrhea that persists > 72 hours despite the use of maximal medical intervention and/or prophylaxis as indicated by good clinical practice and the judgment of the investigator.
- Any grade 4 vomiting or diarrhea regardless of duration.
- Failure to recover from toxicities to be eligible for re-treatment within 4 weeks.
- Any death not clearly due to the underlying disease or extraneous causes, and for any toxicity requiring permanent discontinuation of study drug(s).
- Hy's law, defined as: AST or ALT > 3 x the upper limit of normal (ULN) with concurrent increase in total bilirubin > 2 x ULN without evidence of cholestasis or alternative explanations, (e.g., viral hepatitis, disease progression in the liver, etc.)
- Neutropenic fever

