3.1.6 Combination of Sotorasib with Tarloxotinib

The combination of tarloxotinib with sotorasib is poised to provide highly specific tumor inhibition while targeting the vertical KRAS signaling pathway with minimal toxicity. The combination is unlikely to result in clinically relevant drug-drug interaction (DDI) based on absorption, metabolism, elimination or protein-binding. Tarloxotinib is intravenously administered while sotorasib is a small molecule that is administered orally; no absorption interactions are expected.

Table 2 provides a comparison of the toxicity noted in Phase I/II clinical trials of these two drugs. The safety profile is expected to be generally non-overlapping with the exception of gastrointestinal adverse events that include nausea and diarrhea.

3.1.7 Comparison of Toxicity reported in the individual Phase I/II studies of Sotorasib and Tarloxotinib

Adverse events	Tarloxotinib (n=23)		Sotorasib (n=129)	
	Any grade	>G3	Any grade	>G3
QTc prolongation	60.9%	34.8%	-	-
Rash acneiform	43.5%	4.3%	-	-
Diarrhea	21.7%	4.3%	29.5%	2.3%
Nausea	21.7%	0%	20.9%	1.6%
Fatigue	33.3%	0%	23.3%	2.3%

Vomiting	-	-	17.8%	3.9%
Abdominal pain	-	-	17.8%	3.1%
Dyspnea	-	-	16.3%	2.3%
Cough	-	-	15.5%	0%
Back pain	-	-	14.7%	1.6%
Decreased appetite	-	-	14.7%	1%
Headache	-	-	14.0%	0%
AST elevation	-	-	13.2%	2.3%
anemia	-	-	13.2%	4.7%
dizziness	-	-	13.2%	0%
ALT elevation	-	-	11.6%	0%
Constipation	-	-	10.9%	0%
Pyrexia	-	-	10.9%	0%
Insomnia	-	-	10.1%	0%
Myalgia	-	-	10.1%	0%
Peripheral edema	-	-	10.1%	0%
Arthralgia	-	-	10.1%	1.6%

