6.5.2 Tarloxotinib Dose Modifications

All patients will receive a weekly tarloxotinib infusion at the RP2Dc determined in the safety lead-in portion of the trial administered as a weekly 1-hour IV infusion on Days 1, 8, 15, and

22 of each 28-day cycle until disease progression or unacceptable toxicity. All patients will begin study treatment based on the body weight measured on Day 1 of each cycle (or within 7 days prior [e.g., Day 22 of the prior cycle]). As described above, tarloxotinib dose calculations do not need to be adjusted within a cycle unless the patient has a > 10% change in body weight. Other dose modifications may be required based on QTc prolongation, infusion-related reactions, and other tarloxotinib-related toxicity as described below.

Dose level reductions will be in a step-wise fashion. If a patient requires more than 2 dose level reductions, tarloxotinib will be permanently discontinued.

Hematologic toxicity has not been associated with tarloxotinib administration to date. However, if Grade 3 or 4 neutropenia or thrombocytopenia considered related to tarloxotinib occurs, then the treatment guidelines for non-hematologic toxicity should be followed. Dose modifications for anemia (any grade) or for Grade 2 or less neutropenia or thrombocytopenia are not required.

If a tarloxotinib-related toxicity results in a treatment delay of more than 3 weeks (withholding more than 2 doses of tarloxotinib), patients will be removed from study treatment unless otherwise approved by the Principal Investigator.

Should a dose reduction for sotorasib be required, given the potential for overlapping toxicities and challenges in attributing toxicities to one drug in a combination therapy, a dose reduction in tarloxotinib should also be considered.

Dose level	Sotorasib	Tarloxitinib
0 (full dose)	960 mg PO daily	150 mg/m ² IV weekly
-1	480 mg PO daily	100 mg/m ² IV weekly
-2	240 mg PO daily	75 mg/m ² IV weekly

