7.1.7 Supportive Care

All patients may receive steroid or anti-emetics premedication prior to tarloxotinib infusions. The premedication regimen will be determined by the Investigator and may be adjusted at subsequent infusions based on the signs and symptoms observed during or after prior infusions.

Additionally, patients may be discharged with take-home prophylactic medications.

The tarloxotinib Phase 1 and 2 studies demonstrated that tarloxotinib is associated with non-hematologic toxicities. These included mainly low-grade skin rash and diarrhea typical of that observed with EGFR TKIs. For this reason, prophylaxis and treatment for these toxicities should be considered following institutional guidelines, similar to another EGFR TKI such as erlotinib or afatinib.

Infusion-related reactions were observed in patients receiving tarloxotinib. These reactions were characterized by flushing, urticarial skin rash, pruritus, and hypotension occurring during or immediately following the infusion of tarloxotinib. Patients who experienced an infusion reaction with the first dose of tarloxotinib received prophylactic steroids prior to subsequent doses, which reduced the severity of infusion reactions. Therefore, prophylaxis for drug hypersensitivity reactions that may include a glucocorticoid and an anti-histamine may be considered prior to each tarloxotinib dose according to institutional guidelines.

Nausea and vomiting have occurred in patients in the Phase 1 and 2 studies; therefore, anti-emetic prophylaxis for minimally to moderately emetogenic regimens should be considered after Cycle 1 Day 1 according to institutional guidelines. Prophylaxis against nausea and vomiting in the tarloxotinib studies was based on metoclopramide as a single agent. If a 5-HT3 antagonist is required, palonosetron should be employed, if possible, as it is considered to have the least potential among 5-HT3 antagonists for QT prolongation.

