11.1.2 POPULATIONS FOR ANALYSES

The following analysis sets will be defined for this study.

The **safety analysis set** comprises all enrolled patients who receive any quantity of study treatment, regardless of eligibility. The safety evaluation will be performed based on the first dose of study treatment a patient receives, regardless of the patient's cohort assignment. The safety analysis set will be used for all dosing/exposure and safety analyses.

The **DLT-evaluable population (safety lead-in only)** comprises patients who have either completed the DLT-observation period (1 cycle, 28 days) and received at least 75% of planned doses of the tarloxotinib and sotorasib combination in cycle 1 or have discontinued study treatment or study participation before completing cycle 1 due to a DLT.

The **intention to treat (ITT) analysis set** comprises all patients in the safety analysis set eligible for study inclusion and who meet the inclusion criteria for dose expansion, including eligible safety lead-in patients treated at the RP2D_c. This analysis set will be used for all efficacy analyses.

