13.2 DEFINITION OF ADVERSE EVENT

An AE is defined as any illness, sign or symptom which has appeared or worsened during the course of the study, regardless of causal relationship to the drug under study, experienced by a patient.

All adverse events should be recorded and described in the adverse event database in REDCap. Adverse events also include Grade 3 or 4 abnormal laboratory test results that were not noted in the Screening Phase.

Pre-existing diseases or conditions will not be considered AEs unless there is an increase in the frequency, duration or severity, or a change in the quality, of the disease or condition. Only grade 3 or 4 abnormal lab values that were not noted during the Screening Phase should be recorded; however, any clinical consequences of the abnormality, regardless of grade should be reported as AEs. Hospitalization for elective surgery or routine clinical procedures that are not the result of an AE (e.g., surgical insertion of central line) need not be considered AEs and should not be recorded as an AE. Progression of cancer also will not be considered an AE.

Death should only be entered as the outcome for an AE when the patient's death is at least probably related to the AE (Note: the causal relationship of the AE to the test article is not to be considered in making this decision). If more than 1 AE is possibly related to the patient's death, the outcome of death should be indicated for each such AE.

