13.6 DOCUMENTATION OF ADVERSE EVENTS

The Investigator will monitor and/or ask about or evaluate AEs using non leading questions at each visit or evaluation. The occurrence of all AEs will be documented in the CRF with the following information, where appropriate:

- AE name or term
- When the AE first occurred (start date)
- When the AE stopped (stop date), (or an indication of “ongoing”)
- How long the AE persisted (optional)
- Severity of the AE
- Seriousness
- Actions taken
- Outcome
- Investigator opinion regarding the relationship of AE to the study drug(s)

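### No blood count is scheduled between C1D1 and C2D1, so a silent, short-lived Grade 3-4 cytopenia that prompts no unscheduled count would escape the DLT and DLT-E tallies (probably a small effect)

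*Combined protocol and SAP*

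**What the plan says.** **Criterion.** Section 6.2 makes "Any Grade 3 or 4 thrombocytopenia, anemia and/or neutropenia" a DLT if it is at least possibly attributable to study drug. It sets no duration or symptom condition. Neutropenic fever is a separate criterion.

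**Window.** Section 11.1.2 gives one 28-day cycle as the DLT-observation period.

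**Calendar.** In section 9.2 the CBCD row is marked at screening, C1D1, C2D1, Day 1 of later cycles, end of treatment (EOT) and safety follow-up. It is blank at C1D8, C1D15 and C1D22. CMP, magnesium and phosphorous are marked at all three of those visits.

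**Other detection routes.** The pre-infusion criteria in section 6.5 require electrolytes and an ECG but no blood count. Section 13.6 has the investigator ask about or "evaluate AEs using non leading questions at each visit or evaluation". Section 13.2 adds: "Adverse events also include Grade 3 or 4 abnormal laboratory test results that were not noted in the Screening Phase".

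**Use of the counts.** Section 11.1 declares the RP2D_c if no more than 1 of 6 patients has a DLT. Section 11.3 applies the same event list, as DLT-equivalents (DLT-Es), to the expansion pause rule.

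**Expected risk.** Section 6.5.2: "Hematologic toxicity has not been associated with tarloxotinib administration to date". Section 7.1.7 says that "tarloxotinib is associated with non-hematologic toxicities". The toxicity table in section 3.1.7 lists anemia at 4.7% for sotorasib (column headed >G3, n=129) and has no neutropenia or thrombocytopenia row.

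**The concern.** The plan counts a laboratory event as dose-limiting however briefly it lasts, but between the first infusion and the start of Cycle 2 it schedules no test that could show it. Questioning at visits will not find an asymptomatic cytopenia, and section 13.2 can record a Grade 3-4 result only if a sample was taken. Section 6.5.2 also ties a tarloxotinib action to Grade 3-4 neutropenia or thrombocytopenia, which likewise needs a count.

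The error runs one way: a missed event lowers the DLT or DLT-E count and never raises it. With six patients and a threshold between 1 and 2 events, a single missed event can turn a de-escalation or a pause into a declared RP2D_c.

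**Working it through.** **1. The plan's own figures.** With pause boundaries of at least 2 DLT-Es at n=6, 3 at n=7-9 and 4 at n=10-11, an exact patient-by-patient recursion gives a pause probability of 12.6% at a true rate of 10% and 95.0% at 50%. Section 11.3 states 13% and 95%. The Beta(0.5, 0.5) posterior with a 33% cut and a 50% threshold returns the same boundaries. These figures are correct, but they take every qualifying event as observed.

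**2. What a single count at C2D1 can see.** Assume onset is uniform over 28 days. An episode lasting d days is still present at C2D1 with probability d/28. With counts every 7 days, the chance of catching it is min(1, d/7).

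| Episode (days) | C2D1 only | Weekly |
|---|---|---|
| 3 | 0.11 | 0.43 |
| 5 | 0.18 | 0.71 |
| 7 | 0.25 | 1 |
| 14 | 0.50 | 1 |

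The episode lengths are assumptions; the documents give none.

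**3. Effect on the two rules.** Let o be the rate of all other DLTs and h the rate of hematologic DLTs, taken as independent. Then p = 1 - (1 - o)(1 - h), and the chance of passing the lead-in rule is (1 - p)^6 + 6p(1 - p)^5.

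- Case A: silent transient cytopenias occur in 0.5% or 1% of patients, and all are missed.
- Case B: h = 4.7% (the sotorasib anemia figure), of which 10% or 25% is missed.

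Example, case A at 0.5% and o = 0.15: true p = 1 - 0.85 x 0.995 = 0.1542, so the pass probability is 0.7665. With the silent events missed, observed p = 0.15 and the pass probability is 0.7765.

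Results at o = 0.15:

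| Case | P(at most 1 of 6) | P(pause) | P(pause, given at most 1 of 6) |
|---|---|---|---|
| A, 0.5% | 0.7665 to 0.7765 | 0.2642 to 0.2525 | 0.0400 to 0.0373 |
| A, 1% | 0.7564 to 0.7765 | 0.2761 to 0.2525 | 0.0429 to 0.0373 |
| B, 10% missed | 0.6800 to 0.6898 | 0.3657 to 0.3542 | 0.0673 to 0.0639 |
| B, 25% missed | 0.6800 to 0.7045 | 0.3657 to 0.3370 | 0.0673 to 0.0589 |

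The pass probability rises by 1.0, 2.0, 1.0 and 2.5 points. The unconditional pause probability falls by 1.2, 2.4, 1.2 and 2.9 points, but most of that is the lead-in rule again, because both rules act on 2 or more of the first 6.

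**4. Sensitivity to o.** Over o = 10%, 15%, 20% and 25%, the lead-in gains stay between 0.8 and 2.5 points. The largest fall in the pause probability, given at most 1 of 6, is 0.8 points at o = 15% (6.7% to 5.9%) and 1.2 points at o = 25% (17.6% to 16.4%).

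**The case against.** The strongest reply is that a Day-1 count suits the stated risk. Tarloxotinib is described as free of hematologic toxicity so far, and the only sotorasib figure is for anemia, which would often persist to C2D1 and be counted there. Symptomatic cases can prompt an unscheduled count, and neutropenic fever is caught separately. This stands, and it is why the effect is called small. It does not remove the mismatch: these are single-agent data, and the documents give no cytopenia rate for the combination.

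The sizes above rest on assumed rates. The 4.7% is not limited to 28 days or to attributable events, and trial patients have already had at least a month of a KRAS G12C therapy (section 4.1). Case B therefore probably leans high.

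The decision rules are also buffered. Section 11.3 bases the final RP2D_c on all the data, a pause leads to committee review, and section 11.1.1 lets the RP2D_c be revised during expansion. A shift in a rule probability is not an equal shift in the final dose decision.

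Weekly counts would record brief laboratory-only cytopenias as DLTs. That is a real consequence, but section 6.2 as written already counts them.

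Two stronger readings are tempting. A reader might infer that the criterion is not measured at all within the 28 days. The documents do not support that: C1D1 has a count, an early EOT visit has one, and the 1-day visit window can bring C2D1 to Day 28. A reader might also infer that every transient cytopenia is lost; only those prompting no unscheduled count are.

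**Conclusion.** The point holds in a limited form. Section 6.2 counts attributable Grade 3-4 cytopenias of any duration, and section 9.2 schedules no count between C1D1 and C2D1. The events lost are those that are silent, prompt no unscheduled count, and resolve before C2D1 or an early EOT visit. The recorded DLT and DLT-E counts can therefore only be too low.

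The likely size is about 1 to 2.5 points on the chance of passing the 1-of-6 rule, and at most 0.8 to 1.2 points on a later pause (other DLTs at 15% to 25%). This assumes independence and missed rates that the documents do not supply. A reader might infer a much larger effect by treating a full 5 points of DLT rate as missed: at a true rate of 20%, the pause probability would then fall from 0.395 to 0.252, about 14 points. That needs every such event to be transient and unseen, which is unlikely for anemia.

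Nor does the finding mean that the stated 13% and 95% are wrong; they reproduce. Section 6.2 speaks of "events occurring during treatment with study drugs" with no cycle limit, against the 28 days in section 11.1.2. That affects every DLT criterion and is a separate matter, which adds no weight here.

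Low severity: the case for change rests on the mismatch and the low cost, not on the size.

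**What to change.** Reconcile the hematologic criterion in section 6.2 with the calendar in section 9.2. The simplest way is to mark CBCD at C1D8, C1D15 and C1D22, on draws already scheduled, for both lead-in and expansion patients, since DLT-Es use the same event list.

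**Cost.** Three CBCs per patient and no added visits. For 12 patients that is 3 x 12 = 36 tests. For 24 patients (18 in the lead-in plus 6 more in expansion) it is 3 x 24 = 72. The 24 is not a firm ceiling, because section 11.1 allows levels below DL -2 and patients not evaluable for DLT could add to it.

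**Trade-off.** Short laboratory-only cytopenias would be found and recorded as DLTs, as section 6.2 already requires. If the sponsor does not intend that, the criterion and the calendar still need to be brought into line; how is for the sponsor to decide.

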6.3 DOSE ESCALATION RULES

Dose escalation/de-escalation in the safety lead-in portion of the trial will follow a standard 3+3 algorithm. Please refer to section 11, Statistical Considerations, for additional details.

6.4 DOSE MODIFICATIONS

This study will utilize the CTCAE (NCI Common Terminology Criteria for Adverse Events) Version 5.0 for toxicity and Serious Adverse Event reporting. A copy of the CTCAE Version 5.0.0 can be downloaded from the CTEP home page (<http://ctep.cancer.gov>). All appropriate treatment areas should have access to a copy of the CTCAE Version 5.0.

6.5 TREATMENT AND RETREATMENT CRITERIA

The results of tumor assessments are not required for the initiation of subsequent cycles, but patients must meet the following criteria before receiving each tarloxotinib infusion. **Note:** all ECG dose modifications will be based on the average manually measured QTcF.

- No QTcF of \geq 601 msec during any previous infusion

Note: Patients with QTcF of \geq 501 msec and $<$ 601 msec during or following the prior infusion MUST be dose reduced. If QTcF prolongation is \geq Grade 3, an ECG may need to be repeated more frequently during a patient's visit as clinically indicated, depending on the degree of the prolongation and per institutional standards.

- Check serum electrolytes
 - Pre-infusion magnesium and calcium in normal range, unless an exception is approved by the Principal Investigator.
 - If other electrolytes (e.g., sodium, chloride) are outside of the normal range, patient can receive tarloxotinib infusion if it is deemed safe per Investigator discretion.
 - Pre-infusion serum potassium must be \geq 3.5 mEq/L.
- Pre-infusion ECG: No evidence of second- or third-degree atrioventricular block
 - QTcF interval of $<$ 450 msec
- Skin rash of \leq Grade 2
- Gastrointestinal toxicity of \leq Grade 2
- Any other clinically significant tarloxotinib-related toxicity must return to at least Grade 2.

All patients not meeting retreatment criteria must be discussed with the Principal Investigator and possible dose/schedule modification and/or study treatment discontinuation discussed.

